# Note: Using this R syntax, main effects are also included
# (i.e., tx, t, and t2).
full_model <- lme(jsb ~ tx * t + tx * t2, random = ~1 | id, data = data)
reduced_model <- lme(jsb ~ t + t2, random = ~1 | id, data = data)
```

Alternative approaches and model modifications

Although we hypothesize the models above, it is possible that data-driven modifications will be needed to the model. These include:

- Consideration of an alternative estimator (e.g., REML) and/or bootstrapped confidence intervals
- The possibility the model could be substantially improved by including cubic, etc., effects
- The possibility of random slopes in addition to random intercepts

We have chosen to focus on a simpler model to ease interpretation and to avoid overfitting, but we will adjust the model as needed based on inspection of the results and diagnostics (e.g., inspection of residuals for normality, heteroscedasticity, influential observations).

Mediation analyses to evaluate mechanism

We envision that participants' job seeking will improve as their emotional distress improves, and vice versa. In other words, we hypothesize a bidirectional relationship between job seeking and depression. We will evaluate this using a random-intercept cross-lagged panel⁴ model in *lavaan* in R, using the `missing = "ML"` argument for missing data that allows for ML estimates for missing-at-random data. Each time point will be regressed on the previous time point. Slopes that are equally spaced in time will be constrained to be equal as a means to lower the number of parameters estimated. Because the purpose of this analysis is to evaluate the mechanism of DRIVEN, we will only conduct it in the DRIVEN group. The main outcomes of this analysis will be the magnitude of the cross-lagged regressions – job searching predicting depression, and depression predicting job searching.

Secondary analyses

Analyses of secondary continuous outcomes, and other exploratory analyses, will be done using mixed models, using the same approach as described above.

Because an important secondary outcome is whether the person obtained a job or not, we will also time-to-event analyses (a.k.a., survival analyses) to create hazard curves of "time unemployed". The primary variable of interest will be treatment group, but other exploratory covariates may be added to the model (e.g., do people with higher baseline depression spend more time in unemployment?).

REFERENCES CITED

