an overall sample size of $N = 126$ overall. Power for simple between-group comparisons of continuous outcomes (e.g., job search behavior) was also examined in the *pwr* package of R; these analyses showed 98% power for the DRIVEN vs. self-guided job-seeking group comparison with large effects ($d = 0.8$), and 93% power for smaller effects ($d = 0.7$).

We also planned some auto-regressive analyses, which we anticipate will have high power owing to the large number of repeated measures in the design; power was approximated by considering the number of t and $t + 1$ observations available for associations. Considering all data points (~100 participants times 22 weeks with a prior week available as a predictor), effect sizes as small as $r = .1$ would be detectable (calculations done in *pwr* package), even when missing data were estimated as much as 50% (i.e., half of weeks left incomplete).

We acknowledge that some changes were made to our design after the power analyses were completed (e.g., there are 6 weeks of survey outcomes plus 2 follow ups), but we deemed these changes necessary on practical grounds (e.g., to reduce participant burden) and did not recalculate power. These changes should not imperil statistical power because we have refined our approach to use a simpler model with fewer parameters (i.e., polynomial regression of continuous time, and time \times treatment interaction).

Missing data and outliers

We will approach the analyses from an intent-to-treat perspective. All participants will be included in the mixed modelling, which can be accommodated using the *nlme* package of R. Although we will inspect the data for outliers and influence, we do not plan to drop cases.

Study Timepoints

There is a baseline assessment, six weeks of intervention with weekly surveys, and two follow-up assessments. The baseline assessment will be included as a covariate and not included as part of the outcome. Time will be treated as a continuous variable calculated as “days since baseline”. The mixed effects modelling will include all observations of the Job Search Behavior questionnaire starting from baseline out to the 16-week post-intervention assessment.

The purpose of the two follow-up assessments (8 and 16 weeks) is to (a) provide a period of time for the person to possibly find a job and (b) examine the trajectory of change in the two groups in job search behavior, from during the acute intervention into a 16-week follow-up period.

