Interim analyses to ensure data quality

In order to ensure data integrity and quality, we will conduct limited interim data analyses. The goal of this analysis will be to conduct a “dry run” of data management procedures. We will import these data from REDCap and inspect them for data quality, and to test scoring algorithms for questionnaires. In these interim analyses, some preliminary results may be shared with potential investors and/or sponsors of the DRIVEN program, but these analyses will not be submitted for publication. The definitive analyses of the RCT will be as described below.

Primary analyses

Job Search Behavior: Preparatory and Active Job Searching

Because the surveillance period of this study may be too short to evaluate whether the participants found jobs

or not, the primary outcome measure will be the Job Search Behavior questionnaire, which has two separate subscales for preparatory versus active job searching. We will use a mixed model with random intercepts for each participant, using the maximum likelihood estimator. Time will be included as a continuous variable as described above (i.e., days since baseline). Because baseline is included as a covariate and not part of the outcome, we will include both a main effect of treatment as well as interaction effects with time. We will then fit a corresponding model with no effects of treatment. Treatment will be coded as Control = 0; DRIVEN = 1. In this way, the effect of treatment can be evaluated by comparing the full to the reduced model. In R pseudocode, the model will appear as follows:

```

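### The printed code for the primary model omits the baseline covariate and the maximum likelihood setting that the text promises

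*SAP*

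**What the plan says.** SAP, Study Timepoints, on baseline: "The baseline assessment will be included as a covariate and not included as part of the outcome". The same paragraph then says that the mixed modelling "will include all observations of the Job Search Behavior questionnaire starting from baseline" and runs to the last follow-up.

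SAP, Primary analyses (Job Search Behavior), repeats the role of baseline and uses it to justify the treatment terms: "Because baseline is included as a covariate and not part of the outcome, we will include both a main effect of treatment", together with interactions with time. On the estimator: "We will use a mixed model with random intercepts for each participant, using the maximum likelihood estimator". On the test: "We will then fit a corresponding model with no effects of treatment", so that "the effect of treatment can be evaluated by comparing the full to the reduced model".

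The model is then written out as R pseudocode:

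- full: "full_model <- lme(jsb ~ tx * t + tx * t2, random = ~1 | id, data = data"
- reduced: "reduced_model <- lme(jsb ~ t + t2, random = ~1 | id, data = data"

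The comment above the code lists the implied main effects as tx, t and t2. The software named under Missing data and outliers is nlme. REML appears only under Alternative approaches and model modifications, as an option to consider. Secondary analyses carries the same modelling approach to the secondary continuous outcomes.

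**The concern.** The code is the only place where the terms of the primary model are listed, and it disagrees with the text on two points.

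1. **Baseline covariate.** Neither formula contains one. If the baseline rows are left out of the outcome, as the text requires, the printed model makes no use of baseline data.
2. **Estimator.** Neither call sets one. In nlme, lme() fits by REML when no method is given; this is a property of the software and is not stated in the SAP. The two models differ in their fixed effects, and REML likelihoods are not comparable across such models. The planned treatment test therefore needs ML in both fits.

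A third, smaller point concerns wording. Saying that the modelled observations start at baseline sits badly with saying that baseline is not an outcome. It may only describe the observation window, but it leaves the content of the data argument open.

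At stake is whether the primary model is fixed in advance. Two competent analysts could fit different models from this SAP and report different results.

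**Working it through.** **The SAP's own figures.** For the simple two-group comparison with 50 per group, the noncentrality is d × √(50/2) = 5d on 98 df: 4.0 at d = 0.8 and 3.5 at d = 0.7. Power is 97.7% and 93.4%, which agrees with the stated 98% and 93%. Recruitment also agrees: 50/(1 − 0.20) = 62.5, so 63 per group and 126 in total. No SAP figure is disputed.

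**Text against code.**

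| | Text | Full call | Reduced call |
|---|---|---|---|
| Baseline covariate | yes | absent | absent |
| Treatment terms | main effect and time interactions | tx, tx:t, tx:t2 | none |
| Time terms | continuous | t, t2 | t, t2 |
| Random part | random intercept | random intercept | random intercept |
| Estimator | ML | not set | not set |

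The calls match the text except on baseline and estimator. The treatment test has 3 df.

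**Precision lost without baseline.** Assumptions not in the SAP: total SD 1; 50 per arm; intraclass correlation (ICC) ρ = 0.3, 0.5, 0.7, which is also the correlation of baseline with every later visit; no missing data. The outcome days are 7, 14, 21, 28, 35, 42, 98 and 154, taking the 8- and 16-week follow-ups as counted from the end of intervention.

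The residual variance is 1 − ρ. The between-person variance B is ρ without baseline and ρ(1 − ρ) once baseline is conditioned on. With Z holding 1, t and t², and x the same terms at day 42, h = x′(Z′Z)⁻¹x = 0.248, and

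Var(day-42 effect) = (2/50) × [B + (1 − ρ)h].

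At ρ = 0.5:

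- without baseline: 0.04 × (0.50 + 0.124) = 0.0250, SE 0.158
- with baseline: 0.04 × (0.25 + 0.124) = 0.0150, SE 0.122

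| ρ | SE without | SE with | Variance ratio | 50/ratio |
|---|---|---|---|---|
| 0.3 | 0.138 | 0.124 | 1.23 | 40.5 |
| 0.5 | 0.158 | 0.122 | 1.67 | 30.0 |
| 0.7 | 0.176 | 0.107 | 2.72 | 18.4 |

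With follow-ups read as days 56 and 112, the ratios are 1.23, 1.65 and 2.69.

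**Power of the 3-df test.** For an effect d that is constant from day 7, the noncentrality is d² × 25 × 8/[8B + (1 − ρ)]. At d = 0.4 the numerator is 0.16 × 200 = 32. At ρ = 0.5 this gives 32/4.5 = 7.11 without baseline and 32/2.5 = 12.8 with it, hence power of 60% and 87% (noncentral chi-square).

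| Effect | Without baseline (ρ = 0.3/0.5/0.7) | With baseline |
|---|---|---|
| 0.4 SD, constant | 78/60/47% | 88/87/94% |
| 0.4 SD, linear to day 42, then flat | 69/69/81% | 76/81/94% |
| 0.7 SD, constant | 99.9/98/94% | 100% |

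**Simulation check.** The same design, with 4,000 replicates per setting and ML likelihood-ratio tests, gives 78/59/46% without and 88/86/93% with baseline at a constant 0.4 SD. With no treatment effect, rejection is 5.6/5.2/5.2% without and 5.6/5.5/5.2% with baseline.

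**Estimator.** The REML likelihood contains a determinant of the fixed-effects design, so the difference between the two fits depends on the unit of time. In 600 simulated trials of the printed formulas (ICC 0.6, no effect), the mean REML statistic was −30.2 with time in days, −18.5 in weeks and −2.6 in hundreds of days, against 3 expected; the ML mean was 3.05. At a constant 0.4 SD, the REML comparison rejected in 0%, 0.3% and 17.3% of runs, and the ML comparison in 51.7%. The SAP measures time in days.

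**The case against.** The strongest reply is that the text governs. It states the baseline covariate twice and the estimator once, the code is labelled pseudocode, and REML is only an alternative. Harm arises only if someone lets the sketch override explicit statements. This stands in part: the SAP does not plan a REML comparison, and the REML figures describe what happens if the calls are run as printed. But the SAP presents these lines as the form the model will take, and apart from the two omissions they are complete calls.

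The second reply is that the precision loss depends on which rows enter the data. If baseline rows are kept as a day-0 outcome with no covariate, power at 0.4 SD for the gradual effect is 76.1/81.0/93.6%, against 76.3/81.2/93.8% with the covariate, so almost nothing is lost. For the constant effect it is 76.5/66.1/67.4%, against 88.3/86.5/93.7%, so a loss remains. The arithmetic is right, but this reading contradicts the statement that baseline is not part of the outcome. The figures above apply when baseline rows are excluded.

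Third, the ICC, the baseline correlation and the 0.4 SD effect are all assumed. The largest variance ratio comes from the highest ICC and a single-day contrast, not from the planned test. The SAP's simulation also attaches 0.7 to the time-by-treatment interaction; a constant 0.7 corresponds to its simple group comparison. All of this stands, and it is why a range is shown.

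**Conclusion.** The mismatch is plain on the page: both printed calls lack the baseline term and the estimator setting that the text requires. It should be corrected before analysis, because it concerns the primary model for both primary outcomes and carries over to the secondary continuous outcomes.

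Its consequences are limited. Under ML, type I error is unaffected by leaving baseline out. The cost is precision, small at 0.7 SD and potentially substantial for smaller effects. Its size depends on the assumed correlations, the shape of the effect and the exclusion of baseline rows. The missing ML argument is an omission and not a plan to use REML, but running the calls at the software default would make the planned likelihood comparison invalid. The phrase about observations starting from baseline needs clarification only.

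**What to change.** Write both calls so that they implement the text:

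- full: `lme(jsb ~ jsb_baseline + tx*t + tx*t2, random = ~1|id, data = post_baseline, method = 'ML')`
- reduced: `lme(jsb ~ jsb_baseline + t + t2, random = ~1|id, data = post_baseline, method = 'ML')`

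Here `post_baseline` holds only the rows after baseline. In Study Timepoints, say that the modelled observations start with the first post-baseline survey. Under Alternative approaches, add that any REML fit serves estimates, standard errors or Wald/F tests and not the full-versus-reduced likelihood comparison.

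The cost is two lines of code and two sentences, with no new data.

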STATISTICAL ANALYSIS PLAN

Depression Return to Work Intervention (DRIVEN)

Version 1.0

Sites: Inspiration at Work, Northwestern University, University of Chicago

Version 1.0 Date: 17 July 2024

Principal Investigators: [name], [name], &
[name]

NCT#: NCT06026280

Introduction

Study Background

Unemployment can be a time of high emotional distress; in turn, this emotional distress can interfere with active behaviors needed for finding a job, such as preparing for interviews, networking, revising one's résumé, and researching employment opportunities. Occupational impairment can be part of having a mental disorder (e.g., being unable to work due to major depressive disorder). Thus, interventions are needed that support job seekers during unemployment, which is often associated with high distress.

Study Objectives

The goal of this study is to use a randomized controlled trial (RCT) design to evaluate a six-week intervention (DRIVEN) that provides both job coaching, cognitive-behavior activities, and a mobile app that are intended to help participants cope with unemployment-related distress. The comparison condition is self-guided job seeking in which the participant receives standard job search recommendations by email each week.

The **primary outcome measures are the two subscales of the Job Search Behavior questionnaire – preparatory job search behavior and active job search behavior.** Secondary outcomes include employment status (i.e., whether the person found a job) and symptoms of depression. We will also test the hypothesis that a bidirectional relationship exists between job search behavior and depression using a cross-lagged panel model.

Statistical methodology

Overview

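### The mediation analysis is fitted in the DRIVEN arm alone, so its cross-lagged slopes show a within-arm association and cannot be attributed to DRIVEN

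*SAP*

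**What the plan says.** The Study Objectives section of the SAP states the hypothesis without limiting it to an arm: "We will also test the hypothesis that a bidirectional relationship exists between job search behavior and depression using a cross-lagged panel model". The same section gives the trial's comparator: "The comparison condition is self-guided job seeking".

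The analysis itself stands under the heading "Mediation analyses to evaluate mechanism". It is a random-intercept cross-lagged panel model fitted in lavaan, with maximum likelihood for missing data and a restriction on the paths: "Slopes that are equally spaced in time will be constrained to be equal". The population is then narrowed, with a reason: "Because the purpose of this analysis is to evaluate the mechanism of DRIVEN, we will only conduct it in the DRIVEN group". On what will be reported, the section says: "The main outcomes of this analysis will be the magnitude of the cross-lagged regressions", in both directions between job search and depression.

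The section names no treatment variable, no path from treatment to either variable, no indirect effect and no comparison of slopes between arms. The coding "Treatment will be coded as Control = 0; DRIVEN = 1" belongs to the mixed models under Primary analyses. Those models, extended to secondary continuous outcomes under Secondary analyses, estimate treatment effects in both arms, but nothing links them to the panel model.

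The power section bases its auto-regressive calculation on about 100 participants, 22 weeks each, and states that r = .1 is detectable even with half the weeks missing.

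**The concern.** The SAP gives the wish to study DRIVEN's mechanism as its reason for leaving out the controls. For a mechanism claim, the controls are what is needed. Such a claim says that assignment to DRIVEN changes one variable relative to self-guided seeking, and that this change carries over to the other. The first half cannot be examined when everyone in the model is assigned to DRIVEN. The second half is estimated, but as a general link between search and mood that may be just as strong in people who only receive the weekly emails.

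At stake is the reading of the result. Under this heading and with this stated purpose, non-zero slopes invite the conclusion that the trial has shown how DRIVEN works, although the analysis cannot separate that from the ordinary course of job seeking and mood. For the more general hypothesis in Study Objectives, the restriction discards about half the randomised sample without a reason that applies to it.

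**Working it through.** **1. The plan's own figure.** The only figure in the SAP that bears on lagged analyses is the r = .1 statement. Inputs: about 100 participants x 22 weeks = 2,200 observations; with 50% missing, 1,100; two-sided alpha .05. Treating person-weeks as independent, as the SAP's approximation does, the Fisher-z method for a correlation is:

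power = Phi((z_r - z_c) x sqrt(n - 3)) plus a negligible second tail, where z_r = atanh(r) + r/(2(n - 1)) and z_c is atanh of the critical correlation.

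- n = 2,200: power 0.997.
- n = 1,100: power 0.914; smallest r with 80% power is 0.084.

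The statement reproduces. The sample size section gives 50 per group and 100 in total, so about 100 participants means both arms. The SAP does not name the analyses this power refers to, but the cross-lagged model is the only lagged analysis it describes. Changing nothing except the number of arms, 50 x 22 x 0.5 = 550 observations give power 0.651 for r = .1. That isolates the restriction; the effect of the shorter survey schedule is a separate matter and is not counted here.

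**2. What a one-arm fit can identify.** Let T be treatment. In the DRIVEN arm T = 1 for everyone, so Var(T) = 0 and Cov(T, Y) = 0 for every variable Y. A path from T to depression or to search has no estimate. An indirect effect is a product that includes such a path, so it has none either.

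**3. Dependence on the average effect.** Write Y for one participant's scores on both variables at all waves, and d for a vector of treatment effects by wave, the same for everyone. Then

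Cov(Y + d) = Cov(Y).

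With wave means free, complete-data maximum likelihood chooses the slopes by minimising ln|Sigma| + tr(Sigma^-1 S), where S is the sample covariance matrix. S does not change when d is added, so neither do the slopes or their standard errors. With missing waves the same holds if the missing-data pattern is unchanged, because each free mean absorbs its own element of d.

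Numerical check, with assumed inputs: n = 63 (126/2, taking equal allocation), 7 equally spaced waves, equal lags, true cross-lags -0.10 (depression to search) and -0.15 (search to depression).

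| Same simulated participants | Depression to search | Search to depression |
|---|---|---|
| No DRIVEN effect | -0.1128 | -0.2239 |
| Mean effects growing to about 0.8 SD on search and -0.7 SD on depression | -0.1128 | -0.2239 |

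**4. If effects differ between people.** In a simulated sample of 20,000 with true cross-lags of zero and no average effect, person-specific effects (SD 0.7, growing over time, opposite in sign on the two variables) gave slopes of -0.050 and -0.047. Without that variation they were -0.002 and -0.001. So the slopes can move, but the movement is not a cross-lagged link, and without controls it cannot be traced to DRIVEN.

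**5. Cost of the restriction for the general hypothesis.** The standard error of a common slope is proportional to 1/sqrt(n). One arm against two is 63 against 126 before attrition, or 50 against 100 after. In the best case, sqrt(63/126) = sqrt(50/100) = 0.707, so using both arms reduces the standard error by 1 - 0.707 = 29%.

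**The case against.** The strongest reply is that the SAP asks a narrower question than mediation. Its stated hypothesis is a two-way relationship between job seeking and depression, its reported quantities are the two slopes, and it promises neither an indirect effect nor a proportion mediated. A one-arm model can estimate those slopes as associations. That stands. What it does not rescue is the heading and the stated purpose, which attach the slopes to DRIVEN.

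It can also be said that the randomised contrast is not absent from the plan. The mixed models compare the arms on job search and, as a secondary outcome, on depression. This too stands, and it limits the gap: treatment effects on both variables will be known. But the plan does not join them to the slopes, and a treatment effect on each variable plus an association within one arm is not an estimate of an effect carried from one to the other.

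Three stronger readings are tempting, and the document supports none of them:

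- **That the slopes would be the same whatever DRIVEN does.** This is exact only for a uniform effect, free wave means and unchanged missingness. The SAP does not say how wave means are handled, and step 4 shows that varying effects move the slopes.
- **That the one-arm fit is worthless.** It remains a valid description of association among DRIVEN participants.
- **That the efficacy conclusion is compromised.** The primary outcomes are the two job search subscales, tested in both arms; no primary or secondary result depends on the panel model.

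Finally, a two-group model is larger, and the SAP explicitly wants few parameters. With about 50 to 63 participants per arm that is a real cost.

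**Conclusion.** The point holds, for a supportive analysis: it should be fixed, but it does not touch the primary test. As written, the analysis cannot serve the purpose the SAP gives for it, because treatment does not vary in the data. The slopes measure within-arm association. Their complete independence of the average treatment effect rests on the three conditions stated above; that they cannot be attributed to DRIVEN rests on none of them.

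The restriction is also inconsistent with the rest of the SAP: Study Objectives does not limit the hypothesis to an arm, and the lagged power basis counts both arms. The 29% figure is a best case that requires similar slopes and variances in the two arms. The 0.651 power inherits the SAP's simplification that person-weeks are independent.

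**What to change.** Delete the DRIVEN-only restriction and fit the model in participants from both arms.

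1. **Two-group model by arm.** Compare a fit with cross-lagged slopes equal across arms to one with slopes free. If equal slopes are compatible with the data, report common slopes from all participants. This tests the two-way hypothesis and shows whether the links are specific to DRIVEN. It is not a test of mediation: equal slopes are compatible with full mediation, and with wave means free by arm this model is as insensitive to average effects as the one-arm fit.
2. **If a mediation claim is wanted, a separate pooled model** with randomised treatment as a predictor. It must be separate because treatment is constant inside each group of a model grouped by treatment. Specify it so that the effect of treatment on the mediator at t passes through the lagged path to the outcome at t + 1. If treatment predicts the observed scores freely at every wave, the lags carry only within-person deviations and there is no such path. Report the indirect effects in both directions with bootstrap confidence intervals, and state the assumption of no unmeasured mediator-outcome confounding, which randomisation does not secure.
3. **Otherwise** drop the mediation and mechanism labels and report the slopes as association only.

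The cost is SAP wording and analysis work. No new data are needed if controls complete the same surveys, which the SAP does not state for each wave but which its two-arm mixed models for both variables imply. The drawbacks are a larger model at about 50 to 63 per arm and a mechanism claim that may turn out weaker. The change should be made before outcomes are examined by arm.
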